### **3.2 Secondary objectives:**

- Determine the optimal cut-point  $^{18}\text{F}$ -FES uptake value for distinguishing between ER+ and ER-negative DCIS.
- Determine the test-retest reproducibility of quantitative assessment of tumor  $^{18}\text{F}$ -FES uptake.
- Determine the optimal cut-point  $^{18}\text{F}$ -FES uptake value for distinguishing between low-risk DCIS and intermediate/high-risk DCIS.
- Estimate the association of quantitative  $^{18}\text{F}$ -FES uptake (continuous  $\text{SUV}_{\text{max}}$ ) with research-based Oncotype DX DCIS scores (0-100)
- Measure the upgrade rate to invasive cancer at surgical excision.
- To correlate tumor  $^{18}\text{F}$ -FES uptake with serum estradiol and sex hormone binding globulin levels.

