### **4.1 Eligibility Criteria**

#### **Inclusion Criteria:**

- 4.1.1 Women 18 years of age or older
- 4.1.2 Diagnosis of biopsy-proven DCIS without invasion or microinvasion measuring at least 1.0 cm in diameter by any imaging modality
- 4.1.3 Undergoing diagnostic breast MRI ordered by the referring clinician for staging and extent of disease†

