## 5. RESEARCH DESIGN AND METHODS

### 5.1 Study Design

This prospective, single-arm, observational, single-institutional research study will enroll women with DCIS scheduled for diagnostic breast MRI for preoperative staging/extent of disease evaluation. The proposed work-flow is described in the schema above. Eligible patients will be consented for participation in the research study which will involve the simultaneous acquisition of F-FES PET imaging data during a standard dynamic contrast enhanced clinical breast MRI performed prior to surgical excision. Patients with ER+ DCIS will be offered to participate in an optional sub-study which will involve a second (test-retest) F-FES PET/MRI examination until we have accrued up to 5 patients. The results of the F-FES PET imaging component of the examination will not be used to guide patient management. However, the clinical breast MRI component of the examination will be interpreted and reported with management recommendation as per routine clinical care. Surgical management, radiation therapy, and adjuvant therapy will follow standard of care. A research-based Oncotype DX DCIS score will be obtained from the surgical specimen for research purposes only since this test is currently not frequently used clinically at our institution (only about 1-5% DCIS patients locally).

Patients with DCIS may also participate in this study if a clinical breast MRI has already been performed. In this scenario, a research F-FES breast PET/MRI will be performed on a separate day as the clinical breast MRI exam prior to surgery.

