**Table 2: Study Calendar/Schedule**

Study Activity	Baseline a	Imaging Day b	Clinical Follow-Up c
Informed Consent h	X		
Demographics d	X		
Medical History d	X		
Radiology Reports d	X		X
Pathology Reports (Breast biopsy and final surgical excision) d	X		X
Concomitant Medication Review		X	
Pregnancy Screening		X	
Day of last menstrual period (if premenopausal)		X	
Height and Weight		X	
Blood for Hormone Levels		X g	
 F-FES PET/MRI i		X	
Adverse Event Evaluation e		X	X
Research-based Oncotype DX DCIS Score f			X

- (a) Baseline is defined as the time period from initial subject contact until injection of F-FES.
- (b) Imaging Day is defined as the day of the research F-FES PET/MRI imaging session.
- (c) Subjects' medical records are followed until final surgical excision and clinical determination of adjuvant therapy plan. Any standard of care labs, procedures, and/or imaging exams obtained during this time period will be reviewed. Data regarding recommended adjuvant therapy (radiation and endocrine therapy) will be recorded. There are no protocol requirements during this time frame.
- (d) Clinical data, including age, race/ethnicity, primary breast cancer data (standard clinical histopathology including tumor biomarkers, location, size, and date of biopsy/diagnosis), mammographic breast density, and menopausal status will be recorded from the electronic medical record.
- (e) Adverse events occurring within one day after F-FES infusion will be recorded by the study coordinator who will contact the subject within 1 to 3 days.
- (f) Oncotype DX DCIS score will be obtained from the electronic medical record if performed clinically (only 1-5% of DCIS patients locally expected) and will also be performed as a separate research-based assay using the resection specimen.
- (g) Blood sample collected will be up to 10 mLs total.
- (h) During the COVID-19 pandemic, consent procedures will be conducted by phone, when possible, to minimize face-to-face contact subjects have with the research team. An encrypted copy of the consent form will be mailed or emailed to subjects prior to the scheduled consent phone call.
- (i) Subjects who are unable to undergo a PET/MRI scan will be invited to undergo a PET/CT along with a separate MRI scan

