## 6.5 Criteria for Removal from Study

Enrolled patients will be removed from the study in the following circumstances:

- Subject does not complete the PET/MRI examination per study protocol
- Positive pre-scan pregnancy test
- Subject withdraws consent
- Exclusion criteria are discovered after registration but prior to the PET/MRI examination

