Scatter plots of continuous quantitative  $^{18}\text{F}$ -FES uptake ( $\text{SUV}_{\text{max}}$ ) on the y-axis and research-based Oncotype DX DCIS scores (unitless) on the x-axis will be created to explore the distribution of the measurements. Pearson's or Spearman's rank correlation will be used to evaluate the association between quantitative  $^{18}\text{F}$ -FES uptake and research-based Oncotype DX DCIS score. The correlation coefficient (rho) and 95% confidence interval will be reported.

5. To determine the upgrade rate to invasive cancer at surgical excision.

This percentage will be calculated by dividing the number of patients with invasive breast cancer diagnosed at the time of surgical excision by the number of patients with percutaneous biopsy-proven DCIS in the study.

6. To correlate tumor  $^{18}\text{F}$ -FES uptake with serum estradiol and sex hormone binding globulin levels.

A correlation analysis of serum estradiol and sex hormone binding globulin levels will be performed using Pearson's or Spearman's rank correlation. Scatter plots, correlation coefficients (rho) and 95% confidence intervals will be reported.

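### The upgrade-rate formula counts any retained patient without an excision result as not upgraded, and no confidence interval is planned for it

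*Combined protocol and SAP*

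**What the plan says.** Section 3.2 states the objective: "Measure the upgrade rate to invasive cancer at surgical excision". Section 12.2, item 5, describes the numerator step as "dividing the number of patients with invasive breast cancer diagnosed at the time of surgical excision". The divisor that it then names is not limited in the same way: "by the number of patients with percutaneous biopsy-proven DCIS in the study". Nothing more is said about the estimate, and no interval is mentioned.

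Eligibility (Section 4.1) requires "Diagnosis of biopsy-proven DCIS without invasion or microinvasion measuring at least 1.0 cm in diameter by any imaging modality", so biopsy-proven DCIS describes everyone enrolled and does not narrow the denominator. A planned excision is not an inclusion criterion.

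Section 5.1 says "Surgical management, radiation therapy, and adjuvant therapy will follow standard of care". Note (c) to Table 2 says "Subjects' medical records are followed until final surgical excision and clinical determination of adjuvant therapy plan", and adds of that period: "There are no protocol requirements during this time frame". Excision is thus expected but is not a study procedure.

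Section 6.5 lists four grounds for removal: an incomplete scan, a positive pre-scan pregnancy test, withdrawal ("Subject withdraws consent"), and an exclusion found between registration and the scan. Absence of an excision or of surgical pathology is not among them.

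**The concern.** The numerator and denominator describe different groups. The numerator is limited to patients whose surgical specimen was examined, while the denominator is everyone with the qualifying diagnosis. A patient with no surgical result is not treated as unknown. She is counted as a patient in whom no invasion was found, and that can only lower the percentage.

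No section defines an evaluable set for this endpoint or says how a missing surgical result is handled. Nor does any section say who is in the study for this count: Section 6.2 enrols patients at consent, and Section 6.5 removes some of them later. Two analysts following the plan could use different denominators.

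The missing interval is a separate gap that does not depend on anyone missing surgery. The AUCs, the sensitivity and specificity in item 3, the ICC, and the correlations all have a planned 95% interval. Item 5 is the only numbered secondary item with none. A bare percentage from about 12 patients, particularly 0%, says little without one.

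**Working it through.** **Inputs.** The sample size of 12 comes from Section 12.1. The documents give neither an expected number of upgrades (x) nor an expected number of retained patients without an excision result (u). I take x = 1 to 4 and u = 0 to 3 as assumed ranges.

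**The plan's own figure.** There is no stated figure for the upgrade rate, so the only one to check is N = 12, which was set for the primary correlation (r = 0.73, two-tailed alpha 0.05, 82% power). With Fisher's z, atanh(0.73) = 0.929, and n = ((1.960 + 0.842)/0.929)² + 3 = 12.1 for 80% power. At n = 12, power is 79.6% with plain Fisher z. It is 82.3% with the bias-corrected form, which adds r/(2(n−1)) and matches the stated 82%. I therefore use 12 as the denominator.

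**Formulas.** Planned rate: x/12. Rate among patients with an excision result: x/(12−u). Their ratio is (12−u)/12, so the planned rate is too low by a relative u/12, whatever x is. The exact 95% limits for x out of n are the 2.5% quantile of Beta(x, n−x+1) and the 97.5% quantile of Beta(x+1, n−x).

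**Results for x = 3** (planned rate 3/12 = 25.0%):

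| u | Rate among excised | Absolute shortfall (points) | Relative shortfall | Exact 95% limits, excised |
|---|---|---|---|---|
| 0 | 3/12 = 25.0% | 0.0 | 0% | 5.5 to 57.2% |
| 1 | 3/11 = 27.3% | 2.3 | 8.3% | 6.0 to 61.0% |
| 2 | 3/10 = 30.0% | 5.0 | 16.7% | 6.7 to 65.2% |
| 3 | 3/9 = 33.3% | 8.3 | 25.0% | 7.5 to 70.1% |

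Over x = 1 to 4 and u = 1 to 3, the absolute shortfall runs from 0.8 points (1/11 = 9.1% against 1/12 = 8.3%) to 11.1 points (4/9 = 44.4% against 4/12 = 33.3%).

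**If the target were the whole cohort.** Suppose the intended quantity were the proportion of all 12 who harbour invasive disease. The u unknown results could then be anything from all negative to all positive, so the proportion lies between x/12 and (x+u)/12. With x = 3 and u = 2 that is 3/12 = 25.0% to 5/12 = 41.7%. The planned formula always reports the bottom of this range.

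**Precision with no missing results.** The exact 95% limits are 0 to 26.5% for 0/12, 2.1 to 48.4% for 2/12, and 5.5 to 57.2% for 3/12.

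**The case against.** The strongest reply is that this is a preoperative cohort, so the two denominators will be the same. Section 2 calls excision the conventional treatment, Section 5.1 describes the MRI as preoperative and places the scan before surgery, and the research gene-expression assay needs the surgical specimen. On that reading u is zero and the formula does no harm. This stands as far as it goes: a reader might infer that the rate will be biased downward, and the documents do not support that as a fact. They support only that it is too low if some retained patient has no excision result.

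Two further readings also go too far. A reader might infer that everyone who withdraws or is removed under Section 6.5 is scored as not upgraded. That section removes such patients from the study, and item 5 counts patients in the study, so on the ordinary reading they drop out of the denominator. What is left is an ambiguity. A reader might also take the background mention of a trial of endocrine therapy as a substitute for standard local treatment as a sign that patients here will forgo surgery. That is a different trial. Section 2 leaves avoidance of surgery to later studies, and here scan results do not guide management.

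It is also fair to say that the endpoint is descriptive, with no test or threshold attached. The sampling error at 12 patients far exceeds the shift from one to three missing results. A reader given the counts could compute an interval, and the optimal cut-points and the coefficient of repeatability have no planned interval either.

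Finally, a rate among excised patients has its own limit. If those without excision are mainly at low risk, it overstates the upgrade rate for biopsy-proven DCIS in general. That is why the unexcised number must be shown beside it. None of these points makes the written formula match an objective defined at surgical excision.

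**Conclusion.** The point holds in a limited form. As written, item 5 scores a retained patient without an excision or surgical pathology as not upgraded, and no other section corrects this. The rate is then too low by a relative u/12, or 8.3% per such patient among 12, and it can never be too high relative to the rate among excised patients. The error is zero if every patient is excised with pathology available, which the documents expect. The values of u and x used above are assumptions. The status of patients removed under Section 6.5 is unclear, not shown to be wrong. The absence of an interval stands regardless of u. The matter is minor: a descriptive secondary percentage, with no effect on the primary analysis or the sample size.

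**What to change.** In Section 12.2, item 5:

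- Define the denominator as patients with biopsy-proven DCIS who had surgical excision with final pathology available.
- Report separately the number without an excision or without final pathology, and state whether patients removed under Section 6.5 appear in that number.
- Give the proportion with an exact (Clopper-Pearson) 95% confidence interval.

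The cost is two or three sentences. Table 2 already collects pathology reports from the final excision, so no new data are needed and nothing in patient care changes. The small price is that the rate then applies only to excised patients, which the separate count makes visible.

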### 12.3 Secondary Objectives

To correlate tumor cell density with  $^{18}\text{F}$ -FES uptake on PET/MRI. A strong correlation between tumor cell density and detection by  $^{18}\text{F}$ -FDG PET/CT

imaging has been reported (49). A correlation analysis of tumor F-FES uptake and tumor cell density will be performed using Pearson's or Spearman's rank correlation. Scatter plots, correlation coefficients (rho) and 95% confidence intervals will be reported.

#### 12.4 Evaluation of Toxicity

All subjects will be evaluable for toxicity from the time of injection of F-FES until 24 hours after injection. For this evaluation, the study coordinator will contact the subject within 1 to 3 days after F-FES administration.

### 13. PATHOLOGY REVIEW

#### 13.1 Justification

The pathology of the biopsy-proven breast cancer will be evaluated per the current standard of care (histologic diagnosis, grade, tumor biomarker status). ER status is reported as positive or negative and includes a percentage of cells staining positive as well as intensity of staining. This information will be obtained from the clinical pathology report in the subjects' electronic medical record and will be used to calculate a semi-quantitative Allred score (44). If the information needed to calculate the Allred score is not included in the clinical pathology report, a pathologist on the research study team will review the existing ER IHC slides. If the information needed to determine tumor cell density is not included in the clinical pathology report, a pathologist on the research study team will review the existing H&E slides.

#### 13.2 Required Pathology Materials

Pathology reports will be available through the electronic medical record. Existing pathology slides (ER IHC and H&E) from the breast biopsy used for initial diagnosis will be requested from the Department of Pathology for Allred scoring by the research study pathologist if the information needed to calculate the Allred score is not included in the clinical pathology report.

For the research-based Oncotype DX DCIS score, a study pathologist will review the H&E slides from the surgical specimen and select a block for release to the TRIP Laboratory. We anticipate needing 6 unstained sections per patient specimen for sufficient RNA isolation for the assay.

#### 13.3 Routing

If needed, requested pathology slides will be sent to the research study pathologist.

## **14. RECORDS TO BE KEPT**

The PI will supervise the data collection and management. The following types of data and materials will be collected:

### **14.1 Images**

Images from the PET/MRI examinations will be stored on the local picture archiving and communication system (PACS) (McKesson, San Francisco, CA). The local PACS system is password protected behind the UWHC Department of Radiology firewall.

### **14.2 Regulatory and Consent**

A research chart will be created for each subject. The chart will include the signed consent form, a copy of the subject's experimental bill of rights, and a signed HIPAA form. Research charts will be kept in a locked file cabinet within a study team members secure office. An enrollment log will be maintained. The enrollment log will confirm that informed consent was obtained on each subject. The patient has the right to decline to participate in the study and to request removal from the study at any time. Informed consent will be provided and signed prior to enrollment in the study. Patients may refuse to answer any questions asked during the duration of the study if they are too uncomfortable to answer. All of these potential risks will be described to the patient in the informed consent document.

### **14.3 Confidentiality**

Information about study subjects will be kept confidential and managed according to the requirements of the Health Insurance Portability and Accountability Act of 1996 (HIPAA). Subjects will be assigned a unique study number upon enrollment that will be used to label their research data in lieu of directly identifiable information. All subject data collected during participation in the study will be kept in a locked file cabinet within a secure office or a password-protected database that uses departmental servers and will only be accessible to study team members. After the study is completed, all data will be de-identified for the purposes of research presentations/publications. The study breast MRI examinations will be archived on the standard clinical PACS system which is password protected behind the UWHC firewall. The study data and records will be maintained for up to 5 years after the conclusion of the study, at which point the PI will destroy the key to the coded identifiers, thus permanently anonymizing the data.

## **15. PATIENT CONSENT AND PEER JUDGMENT**

Current FDA, state, federal, and institutional regulations concerning informed consent will be followed.

## 16. DATA AND SAFETY MONITORING

Safety monitoring of research protocols investigating novel PET tracers utilize a combination of tools. These are framed to provide adequate clinical trial oversight ensuring that the research team is complying with the conditions of IRB approval and FDA requirements. The tools enable frequent evaluations of study-related activities, identification of deviations or noncompliance with the conduct of the study or protocol, review of adverse events tracking and reporting, and review of drug production and accountability.

These tools include:

- Study visit checklists – Research Coordinators use study visit checklists, developed in conjunction with the PI, to ensure that all study required procedures and processes are met before, during and after the subject has been enrolled. Items listed on these checklists include informed consent obtained, consent questions answered (and by whom), medications reviewed, MR safety form, etc. These checklists are completed and reviewed by the study coordinator requiring signature approval for each study subject to ensure tight adherence to the protocol.
- Safety monitoring – The safety monitoring of subjects enrolled in the research includes both internal and external safety checks governing the administration of F-fluoroestradiol (FES). Internal monitoring is performed by co-investigators and external monitoring by a team of four physicians, scientists, and staff with the appropriate broad clinical and technical expertise. The internal monitoring plan includes a brief review of each subject visit after it occurs. In this regard, the study team will discuss data quality, F-FES production and administration, and subject compliance and tolerance of research procedures.

The external monitoring plan includes a 4-person committee of physicians, scientists, and staff with the appropriate expertise (nuclear medicine, oncology, research nurse manager, medical physics) that meets annually with representatives from the research team, to discuss research progress, AE reports, as well as other data reports (note-to-file documentation, protocol deviations, reportable events) compiled by the study team. If an AE occurs, an ad hoc committee meeting will be organized to discuss whether the event is considered serious, whether it can be attributed to research procedures, whether it constitutes an unanticipated problem or non-compliance on the part of the study team, and the plan for resolution and a future remediation.

As part of this plan, the monitor(s) will verify that:

- The rights and well-being of human subjects are protected
- Reported study data are accurate, complete, and verifiable from source documents
- The conduct of the study is in compliance with the currently approved protocol, GCPs, applicable regulatory requirements, and guidelines for clinical research studies at the University of Wisconsin-Madison and its affiliates

## 16.1 Risks

### 16.1.1 MRI

The risk from the MRI component of the exam is minimal and is primarily related to claustrophobia and discomfort with positioning. Only staff skilled in the placement of IVs will place IVs for the study breast PET/MRI. Injection of gadolinium contrast has common mild side effects, including nausea, headache, and hives. More serious reactions, while rare, can occur, including allergic reactions. Any significant allergic reaction or contrast extravasation will be monitored and treated appropriately by clinical staff.

All hardware used to obtain MR images is FDA approved and will be used in accordance with the conditions approved by FDA. The investigational software being used in image acquisition is designed to stay within the current guidelines for MRI safety, established by the FDA. In addition, the investigational software does not meet the definition of a Significant Risk Device as outlined by the FDA under 21 CFR 812.3 as being:

- Intended as an implant and presents a potential for serious risk to the health, safety, or welfare of a subject;
- Purported or represented to be for use supporting or sustaining human life and presents a potential for serious risk to the health, safety or welfare of a subject;
- For a use of substantial importance in diagnosing, curing, mitigating, or treating disease, or otherwise preventing impairment of human health and presents a potential for serious risk to the health, safety or welfare of a subject; or
- Otherwise presents a potential for serious risk to the health, safety, or welfare of a subject.

